9.2.2 Inclusion Criteria

The following inclusion criteria were used to select studies contributing to the meta-analysis:

- Phase 3 and 3b/4 studies conducted by BMS or its licensed partners for mavacamten that were initiated or planned to initiate prior to the end of 2023.
- Placebo-controlled, double-blind, randomized studies of mavacamten
- Studies including adult (age \geq 18 years) patients with symptomatic HCM.

Studies are included if they meet all three conditions.

9.2.3 Exclusion Criteria

Not Applicable.

9.3 Variables

9.3.1 Outcomes/Endpoint Variables

The variables in this study are the same as the primary and secondary endpoints defined in Section 9.1.1. The analyses will include first events that occur on-treatment during the placebo-controlled double-blind period for each study, based on internal or external adjudication in the secondary data sources. Please refer to Appendix 1 for the list of Medical Dictionary for Regulatory Activities (MedDRA) terms (Version 26.1) used to define the major CV events included as primary and secondary endpoints.

9.3.2 Exposure/Independent Variables of Interest

The primary analysis will include the treatment group (mavacamten versus placebo) as an independent variable.

9.4 Data Sources

The study will use pre-existing secondary data sources being the five studies identified in a BMS clinical trial repository of Company (or partner) sponsored Phase 3-4 trials.

9.5 Study Size

The primary hypothesis will test the effect of mavacamten against placebo for the primary endpoint. The following hypothesis will be tested:

```
Null hypothesis (H0): HR \ge 2.2 vs. Alternative hypothesis (H1): HR < 2.2 where HR is the hazard ratio of mavacamten relative to placebo.
```

The study will combine evidence from five clinical trials using patient-level data and test the null hypothesis at 0.025 significance level. The primary endpoint null hypothesis will be rejected if the upper bound of the 95% confidence interval around HR, based on stratified Cox proportional hazards model, is less than 2.2.

A noninferiority margin of 2.2 was proposed for this meta-analysis during MAA, justified based on its consistency with the EMA reflection paper⁸ on assessment of CV safety profile of medicinal products that mentions "the absence of signals for increased CV risk" to be a factor of influence in relation to quantification of the CV safety profile in patients. It was acknowledged by CHMP during MAA assessment that the conventionally discussed margin for exclusion of CV harm (e.g. upper confidence limit for relative risk on MACE at 1.8) would not be feasible, and the upper limit of confidence interval (ULCI) for the HR of 2.2 was considered acceptable in the context of its existing acceptable CV safety profile and continued long-term safety monitoring outside of the meta-analysis (EMEA/H/C/005457).

9.6 Data Management/Data Quality Assurance

All aspects of the parent studies will be carefully monitored by the sponsor or its authorized representative for compliance with applicable government regulations with respect to current GCP and standard operating procedures (SOPs).

All statistical analyses (details to be provided in the statistical analysis plan [SAP]) will be conducted using SAS version [9.4] or higher.

All data have been or will be collected under standard clinical trials conditions (ie, GCP maintained), the data have been or will be cleaned and validated, databases with placebo-controlled double-blind periods will have been locked by the time of data collection for the meta-analysis.

The Clinical Operations, Data Management, and Biostatistics departments at the contract research organizations (CRO) will collaborate internally and with the sponsor to ensure that the data collected and analyzed for this meta-analysis are of the highest quality possible and meet the data standards set for the trials. This will be accomplished in part through programmed edit checks which will be reviewed by the statisticians, programmers, and other team members on an ongoing basis to evaluate whether any checks need to be added or any existing checks need to be modified. In addition, periodic reviews of listings of accumulating data, assessment of data query trends and resulting retraining of trial site personnel will be performed to further ensure data quality.

9.7 Data Analysis

The meta-analysis will combine evidence using patient-level data from relevant studies described in Section 9.2 and appropriate statistical methods will be applied, to allow inference to be made to the population of symptomatic HCM patients.

This meta-analysis will be performed within 1 year after the last study is unblinded. At present, EXPLORER-HCM, VALOR-HCM and EXPLORER-CN have completed their double-blind placebo-controlled periods and treatment assignment has been unblinded for this period. ODYSSEY-HCM (ongoing) and MEMENTO (ongoing) are projected to be unblinded by 1Q 2026.

9.7.1 Primary Objective

The primary analysis will include time to the first e-MACE event that occurs on-treatment during the placebo-controlled double-blind period for each study. Patients completing the placebo-controlled double-blind period without any events observed will be censored at the end of the placebo-controlled double-blind treatment period. Patients who prematurely discontinue study or discontinue treatment early without any events observed will be censored at the earliest occurrence of either the last contact date, treatment discontinuation date, or scheduled end of placebo-controlled double-blind treatment period.

The time to the first occurrence of an e-MACE event will be analyzed using a stratified Cox proportional hazards model⁹ with study as a stratification factor and treatment as a fixed effect, to provide the overall hazard ratio (HR) between mavacamten and placebo along with its associated 95% confidence interval.¹⁰

The primary endpoint null hypothesis will be rejected if the upper bound of the two-sided 95% confidence interval around HR, based on stratified Cox proportional hazards model, is less than 2.2. The primary estimand is defined below in Table 9.7.1-1.

Table 9.7.1-1: Estimand definition

	Estimand			
Endpoint Category	Endpoint	Analysis Population	Intercurrent Events	Population-level Summary
Primary objective is to assess the risk of e-MACE in mavacamten group compared to placebo, by evaluating the primary endpoint with a noninferiority margin of 2.2.				bo, by evaluating the
Primary endpoint	Time to first e-MACE event	Safety Analysis Population*	Patients who prematurely discontinue study (including non-CV death) or discontinue treatment, will be censored at the earlier of last contact date or treatment discontinuation date or scheduled end of placebo-controlled double-blind treatment period.	The time to the first occurrence of e-MACE events will be analyzed using a stratified Cox proportional hazards model.

^{*}Safety analysis population is defined as all randomized participants who received at least one dose of study drug with analyses conducted according to the actual treatment received

The number of events and incidence rate for each treatment group will be reported. A forest plot may be used for graphical presentation of the individual treatment effect estimates and confidence interval if appropriate. In addition to the composite endpoints, the number of subjects with an event and the event rate will be tabulated for each type of adjudicated event (i.e., separately for each component: CV death, non-fatal MI, non-fatal stroke, hospitalization for heart failure (HF), hospitalization for arrhythmia, other CV hospitalization (for events other than heart failure or arrhythmia) and appropriate shock therapy from ICD).

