4.6 Variables

The primary outcome variable is defined as time from first dose to the first occurrence of an e-MACE event within the placebo-controlled double-blind treatment period, with

expanded-MACE defined for this study as a composite of adjudicated events of CV death, non-fatal myocardial infarction (MI), non-fatal stroke, hospitalization for heart failure (HF), hospitalization for arrhythmia, other CV hospitalization (for events other than HF or arrhythmia), or appropriate shock therapy from implanted cardiac device (ICD).

The primary analysis will include the treatment group (mavacamten versus placebo) as an independent variable.

The secondary outcome variables are defined as time from first dose to:

- The first occurrence of (4-point) MACE event within the placebo-controlled double-blind treatment period, with MACE defined as a composite of adjudicated event of CV death, non-fatal MI, non-fatal stroke, or hospitalization for HF.
- The first occurrence of MACE-plus event within the placebo-controlled double-blind treatment period, where MACE-plus is defined for this study as a composite of adjudicated event of CV death, non-fatal MI, non-fatal stroke, hospitalization for HF, or hospitalization for arrhythmia, or appropriate shock therapy from ICD.
- All-cause mortality within the placebo-controlled double-blind treatment period.
- CV death within the placebo-controlled double-blind treatment period.
- The first occurrence of each of the following events within the placebo-controlled double-blind treatment period:
 - non-fatal MI
 - non-fatal stroke
 - hospitalization for HF
 - hospitalization for arrhythmia
 - other CV hospitalization (for events other than HF or arrhythmia)
 - appropriate shock therapy from ICD

The analyses will include first events that occur on-treatment during the placebo-controlled double-blind period for each study, based on internal or external adjudication of the secondary data sources.

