EXPLORER-HCM (MYK-461-005) (placebo-controlled, double-blind period: 2018-2020; completed) ⁶ [refer to CSR in eCTD sequence number 0000]	Phase 3, double-blind, randomized 1:1, placebo-controlled, multicenter, international, parallel-group study to evaluate the safety, tolerability, and efficacy of mavacamten compared with placebo in adults ≥ 18 years with symptomatic oHCM	The starting dose of mavacamten was 5 mg once daily. At Week 8 and Week 14, mavacamten dose was up-titrated for individual subjects based on their mavacamten plasma concentration and pharmacodynamic (PD) responses at Week 6 and Week 12, respectively, and according to dose titration protocol. The permissible doses were 2.5 mg, 5 mg, 10 mg, and 15 mg.	 LVOT peak gradient ≥ 50 mmHg during screening as assessed by echocardiography at rest, after Valsalva maneuver or post-exercise and VLVOT gradient ≥ 30 mmHg (confirmed by echocardiography core laboratory interpretation). NYHA Class II or III symptoms at screening Background HCM therapy (e.g., beta-blocker, verapamil, or diltiazem) is allowed. 	A total of 251 subjects were randomized 1:1 into the study, including 123 subjects in the mavacamten group and 128 subjects in the placebo group. Subjects remained in the doubleblind period for 30 weeks followed by 8 weeks of double-blind study drug washout

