9.7.2 Secondary Objectives

The analysis of the secondary endpoints will be descriptive, and no hypothesis testing is planned.

Hazard ratios and corresponding two-sided 95% confidence interval for all secondary endpoints will be estimated using the same meta-analytic approach described for primary endpoint.

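### Events after stopping study drug are excluded for every endpoint, deaths included, and the protocol names no analysis that counts them

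*Protocol*

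**What the plan says.** The primary analysis (protocol Section 9.7.1) is a Cox model stratified by study in the safety population. Event-free patients who leave the study or stop treatment early "will be censored at the earliest occurrence of either the last contact date, treatment discontinuation date" or the scheduled end of the double-blind period. Table 9.7.1-1 makes this the strategy for intercurrent events: "Patients who prematurely discontinue study (including non-CV death) or discontinue treatment, will be censored at the earlier of last contact date or treatment discontinuation date", again with the scheduled end as the outer limit.

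Section 4.6 lists every primary and secondary variable, including all-cause mortality and CV death, and then states: "The analyses will include first events that occur on-treatment during the placebo-controlled double-blind period for each study". Section 9.3.1 repeats the limit for both sets of endpoints. Under Section 9.7.2, hazard ratios for the secondary endpoints "will be estimated using the same meta-analytic approach described for primary endpoint"; they are descriptive, with no test.

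On-treatment is not defined, and no days after the last dose are added. Sections 9.9 and 9.10 name one supplementary analysis, the pooled exposure-adjusted incidence rate by arm. Section 9.9 also allows extra analyses for non-proportional hazards. It does not mention informative censoring.

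**The concern.** A patient who stops drug and has a first event days later, still inside the scheduled double-blind period, is treated as event-free. If patients stop because they are getting worse, censoring is related to the coming event and the Cox estimate no longer has its usual interpretation. This is plausible here. All five trials in Table 9.2.1-1 adjust dose on echocardiographic or pharmacodynamic response, ODYSSEY-HCM (the largest) on ejection fraction. Appendix 1 lists reduced ejection fraction and cardiac failure terms under heart failure hospitalization. The quantity that drives dosing therefore lies close to an endpoint component.

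Mortality is affected most directly. A patient who stops drug in an acute illness and dies shortly afterwards is censored alive. In addition, Table 9.7.1-1 treats non-CV death as a censoring event. Carried over literally, that would remove non-CV deaths from all-cause mortality and leave only CV deaths. The protocol gives no separate rule for mortality.

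The stake is a regulatory safety conclusion that rests on few events. Section 9.9 expects fewer than 12 in four of the five studies and concedes that small changes in the data can change the result.

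**Working it through.** **The plan's own figure.** Section 9.5 will "test the null hypothesis at 0.025 significance level", and Section 9.7.1 says the null "will be rejected if the upper bound of the two-sided 95% confidence interval around HR" is below 2.2. One-sided 0.025 and two-sided 0.05 both give z = 1.960, so the decision rule is consistent. The protocol states no event total or power. For scale, Schoenfeld's formula at a true hazard ratio (HR) of 1 against 2.2 needs 51 events for 80% power and 68 for 90%.

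**Planned exposure (Table 9.2.1-1),** splitting EXPLORER-CN 54/27 and ODYSSEY-HCM 210/210 by their allocation ratios:
- Mavacamten: (123×30 + 56×16 + 54×30 + 50×48 + 210×48)/52 = 18,686/52 = 359.3 patient-years.
- Placebo: (128×30 + 56×16 + 27×30 + 50×48 + 210×48)/52 = 18,026/52 = 346.7 patient-years.
- Ratio r = 359.3/346.7 = 1.037; 964 patients, 706 patient-years.

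**How many uncounted events would matter.** Start from near-equal analysed events, a on mavacamten and b on placebo. Add k uncounted mavacamten events. The upper limit is [(a+k)/b]/r × exp{1.96 √[1/(a+k) + 1/b]}.
- 30 analysed (15/15): k = 3 gives HR 1.16, upper limit 2.30.
- 40 analysed (20/20): k = 6 gives 1.25, 2.25.
- 51 analysed (26/25): k = 9 gives 1.35, 2.26.
- 68 analysed (35/33): k = 14 gives 1.43, 2.23.

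In each case k is the smallest number that takes the limit to 2.2 or above. It assumes that no uncounted events fall on placebo.

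**Direction.** The five trials were simulated (3,000 runs per scenario, stratified Cox). The assumptions are a base hazard of 0.075 per year, the yearly stopping rates shown, and, where stated, a mavacamten hazard raised for 8 weeks after stopping and then back to base. None of these inputs is in the documents.

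| Scenario (stopping per year, mavacamten / placebo) | On-treatment: HR, P(conclude NI) | Treatment-policy: HR, P(conclude NI) |
|---|---|---|
| On-drug HR 1; 10% / 10%; no excess | 1.00, 0.77 | 1.00, 0.79 |
| On-drug HR 1; 15% / 5%; 5-fold after stopping | 1.00, 0.78 | 1.08, 0.72 |
| On-drug HR 1; 15% / 5%; 15-fold after stopping | 1.00, 0.78 | 1.28, 0.54 |
| On-drug HR 2.2; 15% / 15%; no excess | 2.23, 0.027 | 2.14, 0.035 |
| On-drug HR 2.2; 30% / 30%; no excess | 2.23, 0.024 | 2.07, 0.052 |

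Monte Carlo standard errors are about 0.003 to 0.009. In rows 2 and 3 the on-treatment analysis is blind to the excess. In rows 4 and 5 treatment-policy follow-up dilutes a real on-drug harm, and the on-treatment analysis is stricter.

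**A shortcut that overstates the effect.** Suppose 20% of mavacamten and 5% of placebo events fall after stopping. Removing those events but no person-time turns a true HR of 2.2 into 2.2 × 0.80/0.95 = 1.85. With SE = 2/√D, the false non-inferiority probability Φ[(ln 2.2 − ln HR)/SE − 1.96] is 0.088 at D = 50 and 0.136 at D = 100. Censoring also removes person-time:
- Person-time lost in proportion to events (20% and 5%): HR stays 2.2 and the error stays 2.5%.
- Half of that lost (10% and 2.5%): HR = 2.2 × (0.80/0.90)/(0.95/0.975) = 2.01, error 5.1% at D = 50 and 6.7% at D = 100.

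**The case against.** An on-treatment estimand in the safety population is a recognised choice, and it guards against dilution in a non-inferiority safety comparison; the last two table rows bear this out. Table 9.2.1-1 describes dose adjustment, not who stops or why, so informative censoring is plausible but not shown. For e-MACE, a patient who stops drug on a cardiovascular admission has already had the primary event. The admission example therefore bites only for the mortality endpoints, which are descriptive and cannot inflate the 2.5% error. The detailed censoring rule is written for e-MACE, so its reach to other endpoints comes through Sections 4.6, 9.3.1 and 9.7.2. Section 9.6 leaves analysis details to a SAP that is not at hand, and a sensitivity analysis may be there.

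Most of this stands, and it limits the point. A reader might infer that the rule favours non-inferiority as such, or that the error rises to 9–14%. The documents support neither: the direction depends on an unreported excess after stopping, and the larger figure ignores lost person-time. A reader might also infer that the 8 weeks in EXPLORER-HCM ("followed by 8 weeks of double-blind study drug washout") set the right window. That is the washout after scheduled treatment in one of five trials, and the protocol gives no persistence data.

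What does not fall is the rule itself. The protocol fixes it in the primary estimand and in an on-treatment limit stated for all endpoints. A sensitivity analysis in the SAP would not by itself repair the mortality rule.

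**Conclusion.** The point holds as a should-fix and a cheap improvement. The protocol fixes strict on-treatment censoring with no post-dose window, extends the on-treatment limit to all-cause mortality and CV death, and names no analysis that would show whether censoring is informative. Neither on-treatment nor treatment-policy follow-up is uniformly conservative, so the reader of the final report needs both. The size cannot be set from the documents. As few as 3 to 14 uncounted mavacamten-only events (30 to 68 analysed) would overturn a balanced result, but whether any will occur is unknown. The simulated probabilities rest wholly on assumed hazards and stopping rates. For all-cause mortality no assumption is needed: the estimand table's treatment of non-CV death cannot be carried over, and deaths soon after stopping would be lost. The evidence does not support replacing the on-treatment primary estimand.

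**What to change.** - Keep the on-treatment analysis as primary.
- Prespecify a treatment-policy analysis of first e-MACE, counting events regardless of discontinuation up to the scheduled end of the double-blind period or last contact, with the same stratified model, reported beside the primary against 2.2.
- Make that follow-up the main analysis for all-cause mortality and CV death, and state that non-CV death is an event, not a censoring reason, for all-cause mortality.
- Define on-treatment with a window after the last dose whose length the sponsor justifies, cut at the scheduled end of the double-blind period or the first open-label dose.
- Report discontinuations by arm and study, and events after discontinuation.

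The cost is protocol and SAP wording and extra runs on patient-level data that are already being pooled. On the status given in Section 9.7, ODYSSEY-HCM and MEMENTO are not yet unblinded, so the change can precede that. There are two downsides. Off-drug time may dilute the treatment-policy HR, which is why it should stand beside the primary and not replace it. Follow-up or adjudication after discontinuation may also be incomplete in some parent studies, three of which have finished their double-blind periods; completeness should be reported by study.

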9.1.2 Secondary Endpoints

The secondary endpoints are defined as time from first dose to:

- 1) The first occurrence of MACE (4-point), where MACE is defined as a composite of adjudicated event of CV death, non-fatal MI, non-fatal stroke, or hospitalization for HF.
- 2) The first occurrence of MACE-plus, where MACE-plus is defined as a composite of adjudicated event of CV death, non-fatal MI, non-fatal stroke, hospitalization for HF, or hospitalization for arrhythmia, or appropriate shock therapy from ICD.
- 3) All-cause mortality.
- 4) CV death.
- 5) The first occurrence of each of the following events:
 - a) non-fatal MI
 - b) non-fatal stroke
 - c) hospitalization for HF
 - d) hospitalization for arrhythmia
 - e) other CV hospitalization (for events other than HF or arrhythmia)
 - f) appropriate shock therapy from ICD

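### All-cause mortality and CV death count only deaths on study drug, and no analysis regardless of treatment status is planned

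*Protocol*

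**What the plan says.** Protocol 9.1.2 lists "All-cause mortality" as secondary endpoint 3 and CV death as endpoint 4. The abstract (4.6) bounds the former by period: "All-cause mortality within the placebo-controlled double-blind treatment period".

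Three further provisions decide which deaths enter the analysis:

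- Section 9.3.1, for primary and secondary endpoint variables alike: "The analyses will include first events that occur on-treatment during the placebo-controlled double-blind period for each study". Section 4.6 closes with the same restriction.
- Section 9.7.1, body text: "Patients who prematurely discontinue study or discontinue treatment early without any events observed will be censored at the earliest occurrence" of last contact, treatment discontinuation or scheduled end of the double-blind treatment period. The estimand table repeats this and adds non-CV death to study discontinuation: "Patients who prematurely discontinue study (including non-CV death) or discontinue treatment, will be censored".
- Section 9.7.2: hazard ratios "for all secondary endpoints will be estimated using the same meta-analytic approach described for primary endpoint". No mortality-specific event or censoring rule is given, and these analyses are descriptive with no test.

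The only supplementary analysis named (9.9 and 9.10) is a pooled exposure-adjusted incidence rate by arm within the double-blind period.

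**The concern.** All-cause mortality is the one outcome here that needs no attribution of cause. Its value in a harm study depends on counting every death in the comparison period in both arms. A patient who worsens, stops study drug and dies shortly afterwards is, under these rules, censored alive on the day drug was stopped.

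Censoring at treatment discontinuation is unbiased only if stopping is unrelated to the risk of death, given arm and study. That assumption is doubtful when the reason for stopping is deterioration. If such stopping is more common on one arm, the on-treatment hazard ratio can understate or conceal an excess of deaths on that arm. The protocol plans nothing that would reveal this.

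**Working it through.** There is no protocol figure to reproduce: no death rate, death count or power is stated for this endpoint. The check sets the rules side by side and then adds an illustration of scale.

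**Which deaths count towards all-cause mortality**

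1. *CV death on treatment.* An event under every provision.
2. *Non-CV death on treatment.* An event under the endpoint definition (9.1.2, 4.6) and under the 9.7.1 body text, which censors only patients who have had no event. It would be censored only if the table's parenthesis, written for e-MACE, were copied to this endpoint.
3. *Death from any cause after stopping drug, before the scheduled end of the double-blind treatment period.* Not counted. The no-event condition in the 9.7.1 body text might seem to rescue such a patient, but 9.3.1 and 4.6 admit only on-treatment events, so the later death is not an event for the analysis. Section 9.7.1 gives no window after the last dose. If 9.7.2 carries over only the Cox model and not the censoring rule, 9.3.1 still excludes the death.

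So category 3 is lost by a stated rule, and category 2 is left unclear. For CV death the same holds: CV deaths after stopping drug are not counted.

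**Scale**

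Inputs from Table 9.2.1-1 (randomised or planned patients × double-blind weeks):

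| Study | n | Weeks | Patient-weeks |
|---|---|---|---|
| EXPLORER-HCM | 251 | 30 | 7,530 |
| VALOR-HCM | 112 | 16 | 1,792 |
| EXPLORER-CN | 81 | 30 | 2,430 |
| MEMENTO | 100 | 48 | 4,800 |
| ODYSSEY-HCM | 420 | 48 | 20,160 |
| Total | 964 | | 36,712 |

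Maximum patient-years = 36,712 × 7 / 365.25 = 703.6.

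The death rate (0.5 to 2% per year) and the share of deaths that occur off drug (10 to 30%) are assumptions, not document figures. Deaths = 703.6 × rate; deaths not counted = deaths × off-drug share.

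| Assumed rate per year | Deaths in period | Not counted at 10% | Not counted at 30% |
|---|---|---|---|
| 0.5% | 3.5 | 0.4 | 1.1 |
| 1% | 7.0 | 0.7 | 2.1 |
| 2% | 14.1 | 1.4 | 4.2 |

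The absolute numbers are small, but so is the total. Section 9.9 itself warns that with few events the results are sensitive to small changes in the data.

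**The case against.** A reader might infer something stronger: that the table's non-CV-death censoring, carried over by 9.7.2, makes all-cause mortality identical to on-treatment CV death. The protocol does not support that. The parenthesis stands only in the e-MACE row, under the sentence "The primary estimand is defined below in Table 9.7.1-1". Non-CV death is not an e-MACE component, so ending follow-up there is ordinary for that endpoint. In 9.7.2, "will be estimated using the same meta-analytic approach described for primary endpoint" most naturally means the same study-stratified Cox model with each endpoint's own event definition. The protocol also lists all-cause mortality and CV death separately, so it intends them to differ. What remains is that 9.7.2 does not say the parenthesis is switched off, which is worth one clarifying clause.

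A reader might also multiply the 1.5 to 2% annual rate in 9.9 by 703.6 patient-years, get 10.6 to 14.1 events, and take that as the scale of the loss. That rate is for CV death, non-fatal MI and non-fatal stroke combined. It includes non-fatal events and leaves out non-CV deaths, so it does not measure deaths lost.

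The best remaining defence has three parts. First, the on-treatment restriction is stated openly and consistently, so it is an estimand choice and not a contradiction. That is right. Second, details may sit in the SAP, which is not shown. That answers a gap, but here the protocol fixes a rule; an SAP that counted off-treatment deaths would depart from 9.3.1. An SAP definition of on-treatment with a short window after the last dose would recover only the earliest of these deaths. Third, the analyses are descriptive. That is also right, and it limits the weight of the point.

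**Conclusion.** The point holds in this form: all-cause mortality and CV death are on-treatment endpoints, deaths after stopping drug but inside the scheduled double-blind treatment period are excluded by rule, and no analysis regardless of treatment status is planned. The exclusion follows from the text alone. That it could mislead rests on the assumption that stopping drug is sometimes linked to deterioration; the protocol gives no data on this. The direction of any bias depends on which arm has more such stopping.

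The size cannot be derived from the documents; the 0.4 to 4.2 uncounted deaths are an illustration under assumed rates. Alpha, power and the non-inferiority decision on e-MACE are untouched. This is a change that should be made for the mortality results to be readable as safety evidence; it is not a flaw in the primary test.

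**What to change.** In 9.7.2, with a matching exception in 9.3.1 and in the parallel sentence of 4.6:

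- State that for all-cause mortality a death from any cause is an event, so the non-CV-death censoring in Table 9.7.1-1 does not apply to it.
- Add an analysis of all-cause mortality and CV death that counts deaths up to the scheduled end of the placebo-controlled double-blind treatment period, whether or not study drug was stopped. Censor at the date last known alive or at that scheduled end, whichever comes first; for CV death, censor also at non-CV death.
- Keep the on-treatment analysis as a companion and report the two side by side.

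The drafting cost is a few sentences and one extra run of the same model. There are two real costs. Some counted deaths will have occurred off drug, which can dilute a drug effect; this is why the on-treatment version should stay. The analysis also depends on vital status after treatment discontinuation in the five parent trials. The protocol does not describe that follow-up (11.1.1 speaks only of MACE adverse events), so its availability should be confirmed study by study and any incompleteness reported by arm.
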